Furthermore, the responses obtained from this questionnaire allow for the estimation of energy expenditure (METs) during a typical week of physical activity. This information can be valuable for evaluating the overall physical activity levels of a population and contributing to scientific or clinical research aimed at determining the risk of diseases related to sedentary behavior and physical inactivity(92).

According to Bustamante in 2022, METs (Metabolic Equivalent of Task) is the unit of measurement for the metabolic energy index consumed by an individual at rest. It corresponds to 3.5 ml O₂/kg x min, which represents the minimum oxygen consumption required by the body to maintain vital functions. METs are classified into three levels: Very light: < 3 METs/min, which can be associated with activities such as sleeping or sitting. The second Light to moderate: 3 to 6 METs/min, examples of this level of expenditure include gardening or cycling. And finally, intense or vigorous: > 6 METs/min, such as high-intensity exercise (93), (See annex 12).

In 2020, Valdez conducted a study to determine the effect of a physical activity (PA) program on cardiorespiratory capacity, considering METs (Metabolic Equivalent of Task) and metabolic risks in university academics. The overall program focused on cardiorespiratory endurance and included aerobic activities such as walking, swimming, stationary cycling, and dancing. The study results revealed that 50% of overweight subjects improved their condition. Additionally, at the beginning of the protocol, 20% of the population had altered triglyceride levels, however, by the end of the intervention, 100% of the subjects were within a stable range. These findings suggest that a properly structured PA program, adhering to fitness training criteria, can lead to positive outcomes in the population(94).

3. Justification

The prevalence of metabolic disorders has been increasing, especially in developing countries. According to the WHO in 2022, 20% to 50% of the population could be affected by these disorders (51). In Mexico, the prevalence of metabolic disorders is equally evident among higher education students, according to the National Health and Nutrition Survey (ENSANUT) 2022, 72.5% of the population had obesity, 25.5% had hypertension, and 21.1% had some form of dyslipidemia. Additionally, Almazán reported in 2020, that 13.8% of the population had hyperglycemia (5,6,34).

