5.2.2. Specific Objectives

1. To establish the prevalence of metabolic disorders (abdominal obesity, triglycerides, HDL, hypertension, and glucose alterations).
2. To determine and compare the post-intervention level of physical activity using the long version of the International Physical Activity Questionnaire (IPAQ).
3. To determine and compare the post-intervention level of cardiorespiratory fitness through the Queen's College Step Test.
4. Compare post-intervention prevalence levels of metabolic disorders (HDL, triglycerides, abdominal fat, hypertension, blood glucose alterations) in higher education students.
5. Determine the level of association between metabolic disorders and cardiorespiratory fitness pre- and post-intervention.

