6.3. Selection criteria

Table 4. Selection criteria

Inclusion	Exclusion	Elimination
University of Colima students linked to the central campus.	Motor limitations that may hinder the performance of physical exercise.	Musculoskeletal injuries during the study period.
Students aged between 18		Unforeseen Medical Events: Unexpected medical

and 25 years old.	Pregnancy or lactation.	situations that could influence study results, such as hospitalizations, serious illnesses, or surgeries.
Authorization to participate in the project with a signed informed consent.	High Vigorous Physical Activity Level according to the IPA-Q.	Non-Compliance with Follow-Up: Subjects failing to meet a minimum of 80% (19 out of 24 sessions) of the stipulated physical conditioning program time.
Suffer from at least one of the parameters of metabolic disorders or cardiovascular risk (Hyperglycemia, decreased DHL, elevated triglycerides, abdominal obesity or hypertension) following the clinical assessment (Considering the criteria established by the ADA and ATPIII).	To be currently under pharmacological treatment to manage altered metabolic levels.	Initiation of clinical treatment that may affect protocol results, such as medications that reduce alterations.
		Participants who voluntarily withdraw from the study.

Source: self-made.

7. Variable operationalisation.

Table 5. Dependent variables.

Dependent variables	Operational definition	Nature	Scale	Instrument
Glucose Alterations	Fasting plasmatic glucose concentration determination:	Quantitative Continuous Ratio	It is considered an alteration >110 mg/dl	Fasting serum glucose

Abdominal Circumference	Total abdominal perimeter Abdominal obesity based on abdominal circumference.	Quantitative Continuous Ratio	It is considered an alteration when: Males >90cm Females >85 cm	Circumferential measurement with ISAK tape measure
HDL (High-Density Lipoprotein)	Serum concentration of high-density lipoprotein in milligrams per deciliter (mg/dl)	Quantitative Continuous Ratio	It is considered an alteration when: Males < 40 mg/dl, Females < 50 mg/dl	Lipid profile test
Triglycerides	Serum concentration of triglycerides in milligrams per deciliter (mg/dl)	Quantitative Continuous Ratio	It is considered an alteration when: Males >150 mg/dl Females >150 mg/dl	Lipid profile test

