Arterial Hypertension	Subject's systolic and diastolic blood pressure measured in mercury millimeters (mmHg)	Quantitative Continuous Ratio	It is considered an alteration when: Males > 130/85 mmHg Females > 130/85 mmHg	Sphygmomanometer
Physical Activity Level	Physical Activity performed by the subject 7 days before the survey	Qualitative Ordinal	PA: Low, Medium, High	IPA-Q (International Physical Activity Questionnaire)
Physical Fitness Test: Aerobic	Subject's cardiorespiratory capacity using an	Qualitative Ordinal	Very Poor Poor Average	Quee's College Step Test

Capacity	effort test.		Good Excellent Superior	
----------	--------------	--	-------------------------------	--

Source: self-made based on the reference (11,105).

Table 6. Independent variables

Variable	Operational definition	Nature	Scale	Instrument
Aerobic physical exercise	Individually adapted aerobic physical exercise program meeting the WHO 2021 criteria and the FITT Principles.	Quantitative Continuous Ration	57% - 76%	Prescription

Source: self-made.

Table 7. Intervinient variables

Variable	Operational definition	Nature	Scale	Instrument
Age	Chronological age in years	Quantitative Continuous	18 - 24 years	Survey
Sex	Genetically corresponding sex	Qualitative Dichotomous nominal	Male and Female	Survey

Source: self-made.

8. Location for carrying out the protocol

University of Colima's Sports Center (central campus).

9. Study Procedure

Once the project is approved by the Bioethics Committee from the Faculty of Medicine at the University of Colima (Annex 1) and the Ethics Committee from Colima's Regional Hospital (Annex 2), annexing a no-conflict of interest letter (Annex 3), letters of intent will be prepared and sent to the directors of the faculties within the central campus of the University of Colima (Annex 4). Their purpose is to inform them about the project's generalities, obtain permission to share it with the students and address any questions they may have

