condition to conclude their assessments, if not, they will be monitored until their answer is affirmative). Subsequently, after completing sample collection and assessments, the control group (A) will continue with the same dynamics as in the initial weeks. The experimental group (B) will maintain the same exercises (jogging, aquatic activities, and stationary cycling), but their intensity may be adjusted from 64% to 76% of the maximum heart rate if favourable results are obtained from the cardiorespiratory fitness test (*annexe 11*), since this shows the level of evolution of the subject after the initial intervention and thus, the FITT-VP principle in exercise prescription would be fulfilled.

At the end of the last 4 weeks of the aerobic physical exercise program, the same sampling will be concluded; Abdominal circumference (*annexe 7*), arterial pressure (*annexe 8*), blood collection by venipuncture for HDL, triglycerides and glycemia (*annexe 9*), and the Queen's College step test will be performed (3 minutes) (*annexe 10*) (after completing all the tests, every participant will receive refreshments and will be asked if they are in good condition to conclude their assessments, if not, they will be monitored until their answer is affirmative), finishing the proposed intervention protocol.

10. Study flowchart

11. Statistical analysis

The statistical analysis will be conducted using the Statistical Package for the Social Sciences (SPSS) Statistics 26 from Business Machine (IBM). Descriptive statistics will be carried out, including measures of central tendency for the variables of age, sex and IPA-Q. Normality tests will be applied such as Kolmogorov-Smirnov for samples > 50 , and Shapiro-Wilk for samples < 50 . For the levels of triglycerides, glucose, HDL (High-Density Lipoprotein), abdominal circumference, and cardiorespiratory fitness, paired-sample T-tests will be used if the data follow a normal distribution, but if they do not, the Wilcoxon signed-rank test will be employed. To compare the control and experimental groups, independent-sample t-tests will be used if the data is normally distributed, otherwise the Mann-Whitney U test will be used. Likewise, a multivariate analysis will be carried out to relate the influence of physical exercise

on metabolic alterations. A significance level of $p \leq 0.05$ will be considered statistically significant.

12. Ethical considerations

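### Objective 2 compares physical activity, but the plan keeps the long IPAQ only as Low/Medium/High and names no test for it; a weekly MET-minute score from the same form would be more sensitive

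*Combined protocol and SAP*

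**What the plan says.** - **Objective.** Section 5.2.2, objective 2: "To determine and compare the post-intervention level of physical activity using the long version of the International Physical Activity Questionnaire (IPAQ"). It is one of five specific objectives. Physical activity is not part of the hypothesis in section 5.3.
- **Variable.** Table 5 in section 7 lists physical activity level among the dependent variables, defined as "Physical Activity performed by the subject 7 days before the survey". It is typed as qualitative ordinal with the scale "PA: Low, Medium, High". The laboratory measures, abdominal circumference and blood pressure in the same table stay continuous.
- **Entry.** Table 4 in section 6.3 excludes "High Vigorous Physical Activity Level according to the IPA-Q".
- **Analysis.** Section 11 names the IPAQ once: "Descriptive statistics will be carried out, including measures of central tendency for the variables of age, sex and IPA-Q". The list of variables for the paired t-test or Wilcoxon test (triglycerides, glucose, HDL, abdominal circumference, cardiorespiratory fitness) leaves it out. A further sentence compares the control and experimental groups by t-test or Mann-Whitney without naming any variable. A multivariate analysis is mentioned but not specified.
- **Continuous score.** Section 2.8.5 says the questionnaire answers "allow for the estimation of energy expenditure (METs) during a typical week of physical activity". The long form in Annexe 6 asks for days per week and for hours and minutes per day in each domain.
- **Timing.** Annexe 6 has the IPAQ completed before and after the intervention. Section 9 lists it at the first assessment, but not at week 4 or at the end of the programme.

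**The concern.** A comparative objective needs an outcome and a named comparison. Here the outcome is a three-class grouping of a form that records minutes, and no test is tied to it by name. A change within a class is invisible, and a small step across a class limit counts the same as a large one. With 24 people per arm, and supervised exercise three times a week in both arms, the contrast in activity may be modest, so lost sensitivity matters. If the choice between the classes and a MET score is left open, it can also be made after the data are seen. Finally, if the form is not completed at the end of the programme, objective 2 has no follow-up data on either scale.

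**Working it through.** **1. The plan's own figure.** Section 6.2 sizes the trial on triglycerides, not on the IPAQ: n = K(σ₁² + σ₂²)/(μ₁ − μ₂)², with K = 6.2, SDs 22.53 and 12.88, and means 131.31 and 116.90.

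6.2 × (22.53² + 12.88²)/14.41² = 20.1; 20 × 1.2 = 24 per group.

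The figure reproduces. It fixes the 24 per arm used below but says nothing about power for physical activity. The documents give no IPAQ mean, SD, class shares or expected effect, so steps 2 and 3 rest on assumptions.

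**2. Information kept by three classes.** Assume a standard normal score with a location shift between arms, and classes formed by cutting that score. With class probabilities pⱼ and cut points cⱼ, the share of information kept is

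I = Σ [φ(cⱼ₋₁) − φ(cⱼ)]² / pⱼ,

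where φ is the normal density and is zero at the two outer limits.

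| Assumed Low/Medium/High | φ at the two cuts | Sum of terms | Share kept |
|---|---|---|---|
| 33/33/33 | 0.3636, 0.3636 | 0.3966 + 0 + 0.3966 | 0.79 |
| 53.7/36.3/10 | 0.3972, 0.1755 | 0.2938 + 0.1354 + 0.3080 | 0.74 |
| 70/20/10 | 0.3477, 0.1755 | 0.1727 + 0.1483 + 0.3080 | 0.63 |

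The 53.7% is borrowed from section 2.1.4.1, where it is the share of this university's students with deficient activity in a 2013 study. It is not stated to be the IPAQ Low class, so it serves only as an illustration.

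**3. Power at 24 per arm.** Simulation with 4,000 runs per setting, two-sided 0.05: a t-test on the continuous normal score against Mann-Whitney on the same score cut into three classes. Assumed reference-arm shares were 33/33/33, 50/40/10, 70/25/5 and 20/40/40.

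| Standardised difference | Continuous | Three classes |
|---|---|---|
| 0.5 | about 0.40 | 0.29-0.32 |
| 0.8 | about 0.77 | 0.62-0.66 |
| 1.0 | about 0.93 | 0.80-0.85 |

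Matched run by run, the smallest loss is 0.923 − 0.851 = 0.072 (50/40/10, difference 1.0) and the largest is 0.785 − 0.636 = 0.149 (70/25/5, difference 0.8). That is about 7 to 15 points. Neither method adjusts for baseline here, so any gain from adjustment is not included.

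**4. Is the follow-up score collected?** Annexe 6 says the form is given before and after. The closing list in section 9 names abdominal circumference, blood pressure, the blood sample and the step test, and not the IPAQ. The two places disagree.

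**5. Can the score be computed from the documents?** Only in part. Annexe 6 supplies days and minutes. It gives no MET weights. Section 2.8.5 offers broad MET bands, and Annexe 14 lists values for daily activities. A scoring rule has to be named.

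**The case against.** **The between-group sentence may already cover it.** A reader might infer that section 11 plans only description of the IPAQ. The documents do not support that. The between-group sentence excludes no variable, Table 5 makes physical activity a dependent variable, and Mann-Whitney can be applied to ordinal classes. This objection stands. What remains is that the IPAQ is not named, is absent from the paired-test list, and has no baseline adjustment.

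**High is excluded only at entry.** A reader might treat the outcome as having two classes. Objective 2 concerns the level after the programme, when participants may reach High, so a two-class calculation does not describe it. That the exclusion in Table 4 is the same as High in Table 5 is itself an inference. The exclusion narrows the baseline only.

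**The classes fit the wording.** Objective 2 speaks of a level and Table 5 defines one, and a median or mode is a legitimate summary of ordinal data. This also stands: the change is a gain in efficiency and not the repair of a contradiction.

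**The size rests on assumptions.** It does. The normal shift, the simple cuts and the class shares are all assumed, and real MET-minutes are skewed.

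**Conclusion.** The point holds as a low-priority improvement. The plan states a comparative objective, keeps only a three-class outcome and ties no named test to it, although the form can yield a continuous weekly score. Under the assumptions in the working, the classes keep roughly 63-79% of the information and cost about 7-15 power points at 24 per arm. These are illustrations and not the trial's own figures.

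A reader might go further and infer that the class comparison has little chance of answering objective 2. That is not shown: in the same simulation three classes reach 0.80-0.85 at a standardised difference of 1.0, and at 0.5 even the continuous score reaches only about 0.40. Sample size is then the main limit, and it was set on another variable. The disagreement between Annexe 6 and section 9 over the final IPAQ does not depend on any of these assumptions, and the objective cannot be met unless the form is completed at the end.

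**What to change.** 1. **Table 5:** define the objective 2 outcome as total MET-minutes per week from the long IPAQ, and cite the scoring rule (MET weights, data cleaning, class limits).
2. **Section 11:** name the IPAQ in the between-group comparison. Compare arms on a log or rank scale with adjustment for the baseline value, and state the transformation in advance, including how zero values are handled. Report Low/Medium/High by arm as a descriptive table.
3. **Section 9 and Annexe 6:** reconcile the two so that the final assessment list includes the IPAQ.

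**Cost:** wording, scoring of answers the form already collects, and one more questionnaire per participant at the final visit if it was not already intended. The drawbacks are that MET-minutes are skewed, so a transformation must be fixed beforehand, and that the scoring source is not in the present documents and must be added.

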6.1 Study design

Single-blind randomized clinical trial.

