Those who agree will receive an informed consent form (Annex 5) for their respective signatures. They will be informed about the appropriate attire for the study (for women, this includes sports shoes, leggings, and a top or T-shirt, and for men, shorts and a T-shirt), the requirement to fast for a minimum of 8 hours on the data collection day, and the date (Saturdays), time (8:00 am to 12:00 pm) and place (Faculty of Medicine, University of Colima) of the initial tests (these tests will also be considered the baseline for people who are found to have a metabolic alteration).

On assessment day, the project team will execute the following tests: application of the IPA-Q questionnaire (*annexe 6*), abdominal circumference (*annexe 7*), blood pressure (*annexe 8*), blood collection by venipuncture for HDL, triglycerides and glycemia (*annexe 9*), and the Queen's College step test (3 minutes) to determine their cardiorespiratory capacity (*annexe 10*), (after completing all the tests, every participant will receive refreshments and will be asked if they are in good condition to conclude their assessments, if not, they will be monitored until their answer is affirmative).

Once all blood samples are collected, they will be taken to the laboratory at the Faculty of Chemical Sciences, University of Colima, for processing. Simultaneously, data from the other assessments will be synthesized. When the final results from all 5 tests are collected, a sample of 48 subjects will be selected for the protocol, considering the established inclusion criteria (*Table 2*). With this sample, simple randomization will be performed in a new meeting, using sealed envelopes (each containing a letter indicating group assignment that will not be seen by

participants). Participants will draw an envelope and mark it with their names, and they will hand the envelope to the designated person (principal investigator).

At the end of the meeting, the envelopes will be opened by the organizers in the absence of the participants to reveal whether they belong to the (A) control or (B) experimental group. This process ensures single-blind criteria, where participants do not know their group assignment.

[figure not shown]

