After forming the (A) control and (B) experimental groups, they will be divided to provide them instructions for compliance with the exercise program while maintaining single-blind conditions. In the control group (A), the exercise prescription used by Habibzadeh in 2010 will be implemented: which involves walking for 30 minutes at an intensity of 57% to 76% of the maximum heart rate, three times per week (Monday, Wednesday, and Friday) for eight weeks (*annex 11*). They will always be accompanied by a previously trained physical education student (Monitoring the intensity range in which the subjects must be during the session, will be done through the effort perception scale (*Annex 12*), heart rate at 15 seconds multiplied by 4 or the H10 polar monitor) (83). On the other hand, the experimental group (B) will engage in an aerobic exercise program (jogging, aquatic activities, and stationary cycling) lasting 40 to 60 minutes, three times per week (Monday, Wednesday, and Friday) for eight weeks, always under the supervision of the principal investigator. Each participant in the experimental group will receive a structured exercise prescription tailored to their specific condition, considering the established aerobic training ranges (57% to 63% of maximum heart rate) (*annexe 11*). (Monitoring the intensity range in which the subjects must be during the session will be done through the effort perception scale (*Annex 12*), heart rate at 15 seconds multiplied by 4 or the H10 polar monitor).

By the end of the first four weeks, the second round of assessments and samples will be done, taking into consideration: Abdominal circumference (*annexe 7*), blood pressure (*annexe 8*), blood collection by venipuncture for HDL, triglycerides and glycemia (*annexe 9*), and the Queen's College step test will be performed (3 minutes) (*annexe 10*), (after completing all the tests, every participant will receive refreshments and will be asked if they are in good

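### The single-blind claim hides only a letter at the draw: participants will know their program, and the available text masks nobody who takes the week-4 and week-8 readings

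*Combined protocol and SAP*

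**What the plan says.** Section 6.1 gives the design as "Single-blind randomized clinical trial", and both abstracts say that allocation follows a simple-blind criterion. Section 9 gives the mechanism. Each participant draws a sealed envelope, names it and gives it to the principal investigator. Later "the envelopes will be opened by the organizers in the absence of the participants". Section 9 concludes: "This process ensures single-blind criteria, where participants do not know their group assignment". Once the groups are formed, "they will be divided to provide them instructions for compliance with the exercise program while maintaining single-blind conditions".

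Group A walks. Of this group Section 9 says: "They will always be accompanied by a previously trained physical education student". Group B jogs, does aquatic activities and cycles on individual prescriptions, "always under the supervision of the principal investigator".

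On measurement, Section 9 says that on the initial assessment day "the project team will execute the following tests". For weeks 4 and 8 it lists waist, blood pressure, blood sampling and the step test without saying who performs them. Annexe 9 has a health professional draw the blood. Annexe 10 has trained personnel demonstrate the step test.

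**The concern.** Blinding is a property of what people know while outcomes are being generated and read. Opening an envelope in private conceals the letter at the draw and nothing after it. If the report repeats the claim in Section 9, readers will credit the trial with a protection that the described procedure does not deliver.

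The protection that could be kept in an exercise trial is ignorance of group among those who take the readings, and the available text does not provide for it. The stakes are raised by Section 5.3, where the hypothesis is met by an effect on at least one of blood pressure, abdominal obesity, glucose or HDL. Waist is read by hand, and blood pressure may be. A modest shift in one such measure, arising from the reader's knowledge of group, could support the hypothesis without any effect of the program.

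**Working it through.** **What participants can know.** Two statements in Section 9 need to be set side by side: that participants do not know their assignment, and that the groups are separated and instructed in their programs. Annexe 11 (Tables 11 and 12) lists walking on all three days for group A, against jogging, swimming and static cycling for group B. A participant told to walk knows that they walk. What could remain hidden is which program the investigators call control, or what the hypothesis is. The documents do not say whether either is withheld.

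**What assessors can know.** The investigator receives the named envelopes, the organizers open them, and the investigator is present at every group B session. In the text available, Section 9 and Annexes 7 to 10 contain no rule that keeps session leaders from measuring, no masked assessor and no instruction to keep group off forms and tubes. The week-4 step test also decides whether intensity progresses in group B only, so whoever applies that result must know the group.

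**Which outcomes are exposed.**
- Waist: tape at hand-marked landmarks (Annexe 7). Exposed.
- Step-test pulse: palpated for 15 seconds and multiplied by 4 (Section 2.8.5, Annexe 10). Exposed. One miscounted beat is 4 beats/min. By the equations in Section 2.8.5, that moves estimated VO2max by 4 × 0.42 = 1.68 ml/kg/min in men and 4 × 0.1847 = 0.74 in women.
- Blood pressure: depends on the device. Section 2.2.3 describes a stethoscope in the background text, Section 7 lists a sphygmomanometer, and Table 8 budgets a wrist digital monitor.
- Triglycerides, HDL and glucose: laboratory values. Little exposed.

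**Illustration of size, for observer-read outcomes only.** The group size comes from Section 6.2 and reproduces: n = 6.2 × (22.53² + 12.88²) / (131.31 − 116.90)² = 6.2 × 673.50 / 207.65 = 20.11, taken as 20, and 20 × 1.2 = 24 per group.

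Suppose there is no true effect and readings in one arm are shifted by b SD (assumed; no document gives a value). With 24 per group, a normal approximation and a two-sided 5% test (Section 11 does not state sidedness), the test statistic is displaced by b / √(2/24) = b / 0.2887, and the false-positive rate is P(|Z + b/0.2887| > 1.96).

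| Assumed shift b (SD) | Displacement | False-positive rate |
|---|---|---|
| 0 | 0 | 5.0% |
| 0.1 | 0.346 | 6.4% |
| 0.2 | 0.693 | 10.7% |
| 0.3 | 1.039 | 18.0% |

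**The case against.** Several stronger readings are tempting, and the documents do not support them.

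A reader might infer that the investigator, or others who know the allocation, will take the outcome readings. No passage says so. The sentence that gives measurement to the project team describes the initial visit, before randomization, when there is no allocation to know. Baseline readings are therefore protected by timing. The gap is that nothing in the available text prevents unmasked reading at weeks 4 and 8. Staffing details, the consent form and the flowchart are not in the public text and might say more, so the claim must stay at what the available text does not state.

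A reader might also infer that there is no blinding of any kind. Both arms do supervised aerobic exercise three days a week for eight weeks, so participants may not know which program is the comparator. That possibility stands, but it is narrower than the claim in Section 9.

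A third inference is that blood pressure will be read by stethoscope. The text leaves the device open.

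Finally, a reader might treat the supervisor as a cluster and compute an inflated error rate from an intra-supervisor correlation. The documents give no such correlation, and if supervision is part of the program as delivered, the result would not be a false-positive rate for that package. Rotating supervisors between arms is not recommended either: it would spread knowledge of allocation to more staff and could carry program content across arms. What stands is that the supervisor differs by arm, so the comparison is of program plus supervision.

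**Conclusion.** The concern holds in this form. The envelope procedure conceals a letter at the draw and does not leave participants unaware of the program they receive. They can at most be unaware of which program is the control, or of the hypothesis. The available text provides no masking of those who measure at weeks 4 and 8. This affects waist, the step-test pulse and, depending on the device, blood pressure. It has little bearing on triglycerides, the outcome used to size the trial, or on HDL and glucose.

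The size of any bias cannot be derived from the documents. The rates of 6.4%, 10.7% and 18.0% rest wholly on assumed shifts of 0.1, 0.2 and 0.3 SD, on 24 analysed per group and on a two-sided 5% test. They show sensitivity and are not a prediction. The wording should be corrected and the readings masked before the week-4 assessments.

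**What to change.** 1. In Sections 6.1 and 9 and in both abstracts, replace the claim that participants do not know their assignment with a statement that they know their program. If true, add that they are not told which program is the control or what the hypothesis is.
2. At weeks 4 and 8, have waist, blood pressure and step-test pulse taken by existing team members who lead no sessions and do not hold the group list. Put only a study code on forms and tubes.
3. State as a limitation that the supervisor differs by arm, so that the trial compares program plus supervision.

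The cost is wording and a rota, with no added participants, visits or tests. It assumes that enough team members are free of session duties, which the available text does not confirm. The downsides are some scheduling effort and that the trial can no longer be described as participant-blind.
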